5.6.4 Follow-up

A member of the study team will contact the subject via telephone approximately 30-40 days after surgery to ask about adverse events and to inquire about urinary tract infection and voiding problems. Subjects will be asked about diagnosis of urinary tract infection since leaving the hospital, and chart review will be performed by study personnel to ascertain the diagnosis of urinary tract infection.

As part of standard of care, most subjects will also have a scheduled post-operative follow up visit in the General Surgery clinic with their surgeon, usually 2-3 weeks following the date of surgery. In general, if a patient is discharged from the hospital

with an IUC, it is standard to have the patient follow up in the Urology Voiding Clinic; however, this would be outside of the scope of this study protocol.

5.6.5 Final study encounter

The final study encounter will be the follow up phone call on or around postoperative day #30 for all subjects (30-40 days after surgery). A study team member will contact the subject via telephone to ask if he/she has been treated for a urinary tract infection since discharge from the hospital (in order to capture UTIs treated outside of the UW system), and to inquire about adverse events since discharge from the hospital.

5.6.6 Early termination visit

If a subject wishes to terminate their enrollment in the study early, no visit will be required, and this decision will have no bearing on the individual's clinical care. If enrollment is terminated after surgery, then the subject will not be replaced. If enrollment is terminated prior to surgery, the subject will be replaced.

6.0 REGISTRATION PROCEDURES

All subjects will be registered prior to beginning the protocol treatment. The following information will be included in registration:

Subject name, address, telephone number, birth date, sex, race Primary disease site, planned operation Date on study Date randomized Staff physician Protocol number

7.0 TREATMENT PLAN

7.1 Administration Schedule

7.1.1 Treatment ARM A-tamsulosin:

Tamsulosin 0.4mg capsule orally one time per day, to be taken 30 minutes after dinner or before bed starting 7 days before surgery and continuing for 0-6 days post-operatively. Outline of schedule:

Day 1: tamsulosin 0.4mg in the evening Day 2: tamsulosin 0.4mg in the evening Day 3: tamsulosin 0.4mg in the evening Day 4: tamsulosin 0.4mg in the evening

> Day 5: tamsulosin 0.4mg in the evening Day 6: tamsulosin 0.4mg in the evening Day 7: tamsulosin 0.4mg in the evening Day 8: surgery Day 8: tamsulosin 0.4mg in the evening (same day as surgery) if the subject has not yet completed the bladder management protocol Day 9-14: tamsulosin 0.4mg in the evening until up to 24 hours after the subject has an indwelling urinary catheter replaced (at which time the protocol stops) or the subject completes the bladder management protocol (has voided twice consecutively with a post-void residual <200mL). The minimum number of total doses is 7; the maximum number of total doses is 14. The 14th dose will be the final dose regardless of bladder function. No subjects will be discharged from the hospital on study medication.

7.1.2 Treatment ARM B—placebo:

Placebo capsule orally dosed exactly as outlined above for Treatment ARM A

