4.2 Eligibility Criteria

4.2.1 Inclusion Criteria

Patients must be 18 years of age or older, English-speaking, able to provide informed consent, and scheduled to undergo an elective, complex intra-abdominal operation with a planned postoperative inpatient stay of at least 1 night. Eligible operations will include any of the following operations approached via any operative approach (i.e. open, laparoscopic, hand-assisted laparoscopic, singleincision laparoscopic, or robotic):

- 4.2.1.1 Partial colectomy
- 4.2.1.2 Total abdominal colectomy
- 4.2.1.3 Proctocolectomy
- 4.2.1.4 Low anterior resection
- 4.2.1.5 Abdominoperineal resection
- 4.2.1.6 Restorative proctocolectomy/IPAA
- 4.2.1.7 Proctopexy (transabdominal) for prolapse
- 4.2.1.8 Intestinal stricturoplasty
- 4.2.1.9 Lysis of adhesions
- 4.2.1.10 End or diverting colostomy reversal
- 4.2.1.11 lleostomy reversal
- 4.2.1.12 Closure of enterocutaneous, enteroenteric, or enterocolic fistula
- 4.2.1.13 Partial or complete gastrectomy
- 4.2.1.14 Small bowel resection
- 4.2.1.15 Small bowel diversion/ostomy

Post-Op Urinary Retention Protocol

Version: 5.0, December 8, 2017 Page 6 of 32

- 4.2.1.16 Large bowel diversion/ostomy
- 4.2.1.17 Pancreaticoduodenectomy
- 4.2.1.18 Pancreatectomy
- 4.2.1.19 Hepatectomy
- 4.2.1.20 Gastric bypass
- 4.2.1.21 Sleeve gastrectomy
- 4.2.1.22 Nissen/Dor/Toupet fundoplication
- 4.2.1.23 Transabdominal adrenalectomy
- 4.2.1.24 Splenectomy
- 4.2.1.25 Complex abdominal wall hernia repair (i.e. Rives-Stoppa type repair, large laparoscopic ventral hernia repair)
- 4.2.1.26 Exploratory laparotomy
- 4.2.1.27 Other comparable complex intra-abdominal operations
- 4.2.2 Exclusion Criteria
 - 4.2.2.1 Less than age 18
 - 4.2.2.2 Allergy or contraindication to tamsulosin
 - 4.2.2.3 Serious sulfa allergy
 - 4.2.2.4 Current use of alpha blocker (alfuzosin, doxazosin, prazosin, silodosin, terazosin, verapamil, tamsulosin, phenoxybenzamine) or oral alpha agonist (midodrine)
 - 4.2.2.4.1 Initiation of one of these medications during the intervention phase of the study will result in subject withdrawal from the study.
 - 4.2.2.5 Current warfarin use
 - 4.2.2.6 Pre-existing indwelling urinary catheter, suprapubic catheter, or urostomy
 - 4.2.2.7 End stage renal disease or dialysis-dependence
 - 4.2.2.8 Sitting systolic blood pressure in the upper extremity of less than 100mmHg at time of eligibility screening
 - 4.2.2.9 Presence of orthostatic hypotension at the time of eligibility screening

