5.6.3 Treatment period

Treatment will start 7 days prior to scheduled surgery and will continue postoperatively for up to 7 days while the subject is still in the hospital (for a total of 14 doses). A member of the study team will contact the subject via telephone as a reminder on the day that treatment is to be initiated. If a subject discontinues study treatment (chooses to withdraw from the study) prior to their scheduled surgery, the subject will be discontinued and replaced, and reason for withdraw from study will be noted. Data will continued to be collected for these subjects and their data will be included on an intent-to-treat basis, but they will be replaced for sample size. If the subject discontinues study drug any time after their surgery, the subject will be followed with intent to treat and will not be replaced. If a subject's planned surgery is postponed PRIOR to initiation of treatment but is rescheduled to within 30 days of when the subject was randomized, then the subject may stay enrolled in the trial, will keep their same treatment assignment, and will be given a new start date for treatment (7 days before their rescheduled surgery date). If, however, the surgery is postponed or cancelled AFTER initiation of treatment, then the subject will be taken off treatment and discontinued from the study. If the subject has not yet initiated treatment and their surgery is rescheduled to a date that is more than 30 days from the date of randomization, the subject will be discontinued.

Once a subject completes the bladder management protocol (is voiding spontaneously and completely—specifically, 2 consecutive voids with PVR less than 200mL) OR requires replacement of an IUC, the treatment will be discontinued within 24 hours, and the protocol is complete. The protocol may be completed as early as POD#0. The maximum number of days of treatment will be 14 (up until POD#6, i.e. last dose given in the evening of POD#6). No subjects will be discharged from the hospital on study medication.

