7.5 Duration of Therapy

Treatment will be discontinued within 24 hours of the subject's completion of the bladder management protocol with return of normal bladder function (2 consecutive voids with PVR less than 200mL) or requirement of IUC re-insertion for urinary retention. The maximum number of doses (days) of treatment is 14. If ongoing urinary retention is present, further management

will be deferred to the treating physician team. This sometimes involves initiation of a short course of alpha-blockers in conjunction with IUC, followed by a spontaneous voiding trial.

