Screening for adverse events, time 1 of 3	Study personnel will ask subject about treatment-emergent adverse events occurring during the preoperative phase of intervention	Study day 8, pre or post operatively	Study team member
Operation (SOC)	Elective inpatient complex intra- abdominal surgery as scheduled	Study day 8	Surgeon
Post-operative treatment with study drug (R)	Dosing of tamsulosin or placebo as described in section 7.1	Study days 8-14, or discontinued prior to day 14 based on completion of bladder management protocol or re-insertion of IUC	Administered by subject's RN
Bladder management protocol (see appendix) (SOC)	Monitoring of bladder volume via supra-pubic ultrasound, measurement of post- void residual volume, intermittent catheterization as needed	Postoperatively, while inpatient (Days 8-14)	Subject's RN
Screening for adverse events, time 2 of 3	Study personnel will perform review of the	From day of surgery until 48 hours after	Study team member

Component	Description	Timing	Contact points
	EMR to abstract AEs	completing the	
	occurring during the	intervention	
	postoperative phase of		
	intervention		
	Telephone call to	30-40 days after	Study team
Final study visit (R)	subject by study team personnel	surgery	member
	Study personnel will	30-40 days after	Study team
	ask subject about	surgery via telephone	member
	treatment-emergent	call, will be combined	
Screening for adverse	adverse events	with inquiry about UTI	
events, time 3 of 3 (R)	occurring during the	(see below)	
	post-intervention		
	phase of trial (up to 30		
	days after surgery)		
	Telephone call to	30-40 days after	Study team
Inquiry about diagnosis of UTI (R)	patient 30 days after	surgery via telephone	member
	surgery to inquire	call (will be combined	
	about whether the	with above phone	
	patient has been	call)/chart review	
	treated for a UTI since		
	surgery; chart review		
	for UTI diagnosis within		
	our institutional EMR		

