9.0 DRUG FORMULATION AND PROCUREMENT

9.1 Tamsulosin hydrochloride (NDC 0597-0058-01)

- 9.1.1 Other names: FLOMAX
- 9.1.2 Classification: alpha_{1A} adrenoceptor antagonist
- 9.1.3 Mode of Action: Tamsulosin works by blocking alpha_{1A} adrenergic receptors in the prostate, prostatic urethra, and bladder neck, which results in relaxation of the smooth muscles in the bladder neck and prostate, thereby reducing bladder outlet obstruction.
- 9.1.4 Storage and stability

Stored at 25 degrees Celsius (77 degrees F); excursions permitted to 15 degrees C to 30 degrees C (59 degrees F to 86 degrees F)

9.1.5 Dose specifics: 0.4mg orally dosed one time per day, 30 minutes after a meal, in the evening

- 9.1.6 Preparation: capsule
- 9.1.7 Route of administration: orally; capsules should not be crushed, chewed, or opened
- 9.1.8 Incompatibilities
 - 9.1.8.1 Other alpha-adrenergic blockers

Per package insert: "The pharmacokinetic and pharmacodynamic interactions between FLOMAX capsules and other alpha-adrenergic blocking agents have not been determined. However, interactions may be expected and FLOMAX capsules should NOT be used in combination with other alpha-adrenergic blocking agents." Patients taking concomitant alpha blockers (including verapamil, which has alpha blockade action at therapeutic doses) will be excluded from the study.

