9.1.8.3 Warfarin

Per package insert: "A definitive drug-drug interaction study between tamsulosin hydrochloride and warfarin was not conducted. Results from limited *in vitro* and *in vivo* studies are inconclusive. Therefore, caution should be exercised with concomitant administration of warfarin and FLOMAX capsules." We will exclude patients taking warfarin.

9.1.8.4 Strong inhibitors of CYP3A4 (boceprevir, clarithromycin, conivaptan, grapefruit juice, indinavir, itraconazole, ketoconazole, lopinavir, nefazodone, nelfinavir, posaconazole, ritonavir, saquinavir, telaprevir, telithromycin, voriconazole) and CYP2D6 (bupropion, fluoxetine, paroxetine, quinidine)

It is recommended that doses higher than 0.4mg daily should not be used in combination with strong inhibitors of CYP3A4 or CYP2D6 and that caution should be exercised when using tamsulosin in combination with such drugs. Studies have demonstrated an increased AUC and C_{max} when tamsulosin is taken in combination with strong inhibitors of CYP2D6 or CYP3A4, but these increases have been shown to still fall equivalently or below the higher U.S. dosage of 0.8mg daily. One study specifically examining clinical effects (i.e. orthostasis) of

concomitant tamsulosin/paroxetine and tamsulosin/ketoconazole found no significant clinical effect of these medications being co-administered. Patients taking strong inhibitors of CYP3A4 or CYP2D6 will not be excluded from the study, however they will be advised about potential increased risk of side effects.

- 9.1.9 Availability: commercially available
- 9.1.10 Side effects (reported in package insert; data derived from two U.S. clinical trials (US92-03A and US93-01)^{7,8}:

	Tamsulosin 0.4mg	Placebo
	(n=502)	(n=493)
Body as whole		
Headache	97 (19.3%)	99 (20.1%)
Infection	45 (9.0%)	37 (7.5%)
Asthenia	39 (7.8%)	27 (5.5%)
Back pain	35 (7.0%)	27 (5.5%)
Chest pain	20 (4.0%)	18 (3.7%)
Nervous System		
Dizziness	75 (14.9%)	50 (10.1%)
Somnolence	15 (3.0%)	8 (1.6%)
Insomnia	12 (2.4%)	3 (0.6%)
Libido decreased	5 (1.0%)	6 (1.2%)
Respiratory System		
Rhinitis	66 (13.1%)	41 (8.3%)
Pharyngitis	29 (5.8%)	23 (4.7%)
Cough increased	17 (3.4%)	12 (2.4%)
Sinusitis	11 (2.2%)	8 (1.6%)
Digestive System		
Diarrhea	31 (6.2%)	22 (4.5%)
Nausea	13 (2.6%)	16 (3.2%)
Tooth disorder	6 (1.2%)	7 (1.4%)
Urogenital System		
Abnormal ejaculation	42 (8.4%)	1 (0.2%)
Special Senses		
Blurred vision	1 (0.2%)	2 (0.4%)

Table reproduced (with modification) from Flomax package insert.

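### A study capsule may be given for up to 24 hours after an indwelling catheter is replaced, and no rule requires study drug to stop before a rescue alpha-blocker is started

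*Combined protocol and SAP*

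**What the plan says.** All references are to the combined protocol and SAP.

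- **Stopping study drug.** Section 7.1.1 allows, for days 9 to 14, "tamsulosin 0.4mg in the evening until up to 24 hours after the subject has an indwelling urinary catheter replaced". Section 5.6.3 says that when a subject "requires replacement of an IUC, the treatment will be discontinued within 24 hours, and the protocol is complete". Section 7.5 repeats the 24-hour limit. The section 8.0 schedule describes postoperative dosing as running to day 14, or "discontinued prior to day 14 based on completion of bladder management protocol or re-insertion of IUC".
- **Rescue.** Section 7.5 leaves persisting retention to the treating team and adds: "This sometimes involves initiation of a short course of alpha-blockers in conjunction with IUC". It gives no start time, interval or cross-reference to another rule.
- **Incompatibility.** Section 9.1.8.1 cites the package insert: "interactions may be expected and FLOMAX capsules should NOT be used in combination with other alpha-adrenergic blocking agents". Patients already on an alpha-blocker are excluded for this reason. Section 9.1.8.4 advises against more than 0.4 mg of tamsulosin a day with strong CYP3A4 or CYP2D6 inhibitors, but keeps patients on those inhibitors eligible.
- **Rule during the study.** Section 4.2.2.4 lists the excluded drugs, tamsulosin among them, and 4.2.2.4.1 says: "Initiation of one of these medications during the intervention phase of the study will result in subject withdrawal from the study".
- **Follow-up.** Under section 5.6.3, if a subject "discontinues study drug any time after their surgery, the subject will be followed with intent to treat and will not be replaced".

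**The concern.** The permitted capsule and the foreseen alpha-blocker can fall in the same day. The treating team is blinded, so it cannot tell whether the capsule was active. A tamsulosin-arm subject could then receive two alpha-blocking doses within hours, soon after major abdominal surgery, with everyone following the plan.

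The plan takes hypotension seriously elsewhere. It excludes a sitting systolic pressure below 100 mmHg and orthostatic hypotension at screening (4.2.2.8, 4.2.2.9), expects more dizziness and orthostasis on tamsulosin (10.8.2.2), and makes syncope a stopping criterion (10.6, 13.1). Against that, the capsule has little apparent purpose, because section 5.6.3 treats the protocol as complete once the catheter is replaced.

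**Working it through.** No rate or sample-size calculation bears on this point. The check is a count of doses and a comparison of the possible sequences.

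**1. The plan's dose range (7.1.1).** Evenings of days 1 to 7 give 7 doses. Evenings of days 8 to 14 give up to 7 more. 7 + 7 = 14. This reproduces the stated minimum of 7 and maximum of 14.

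**2. Capsules permitted after IUC replacement.** Dosing is once each evening.
- Fixed dosing hour: 24 h window / 24 h interval = 1 dose time. The count is 0 if the drug is stopped at once or dose 14 has been given.
- Variable dosing hour: section 7.1.1 allows dosing after dinner or before bed. Assume 18:00 to 22:00. With the catheter replaced at 19:00, a capsule at 21:00 and the next at 18:30, the second comes 23.5 h after replacement, so 2 fall in the window. This is an edge case.
- The earliest such capsule is 7 + 1 = dose 8, on the day of surgery; the latest is dose 14.

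**3. The two possible orders.**

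| Sequence within 24 h of IUC replacement | What the plan provides |
|---|---|
| Alpha-blocker first, capsule due later | 4.2.2.4.1 is triggered by the start of the alpha-blocker; no later capsule should follow |
| Capsule first, alpha-blocker hours later | Capsule is permitted; 4.2.2.4.1 acts only once the second drug has been started |

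Only the second row is open. In the first row there is one uncertainty: 4.2.2.4.1 applies in the intervention phase, and 5.6.3 calls the protocol complete when the catheter is replaced, so whether the 24 hours belong to that phase is unclear.

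**4. Dose if the rescue drug is tamsulosin.** Section 7.5 names no agent or dose; assume 0.4 mg. Then 0.4 + 0.4 = 0.8 mg in the day. Section 9.1.8.4 says of raised exposure with strong inhibitors that "these increases have been shown to still fall equivalently or below the higher U.S. dosage of 0.8mg daily", so 0.8 mg is a recognised dosage for most subjects. For subjects on a strong inhibitor it is above the 0.4 mg that the same section recommends as the ceiling.

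**5. Effect of stopping at IUC replacement.** Replacement on day 8 before the evening dose leaves 7 doses, the stated minimum. Replacement after the day 14 dose leaves 14. The range of 7 to 14 is unchanged.

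**6. Interval if rescue waits for the next evening dose time.** With a fixed hour this is 24 h after the last capsule, if none was missed. With the assumed 18:00 to 22:00 range it is 20 h (22:00 to 18:00) to 28 h (18:00 to 22:00).

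**The case against.** The strongest reply is that section 7.5 is already sequential. It discontinues treatment, states the maximum, and only then turns to ongoing retention and the alpha-blocker. Nothing places the start of rescue inside the 24 hours, which may simply be time allowed to act on the stop. This largely stands: it is the natural reading. It is not a requirement, however, and the text gives neither an order nor an interval.

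Three stronger readings are tempting, and the documents support none of them.

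- A reader might infer that the plan directs two alpha-blockers together. It does not; the capsule is optional and the rescue occasional.
- A reader might infer that section 8.0 contradicts 7.1.1 by requiring an immediate stop. It names the event on which discontinuation is based and treats completion of the bladder protocol the same way, so it sets a trigger and no timing.
- A reader might infer that the study has no safeguard. Rule 4.2.2.4.1 covers rescue given first, and adverse events are abstracted from the record until 48 hours after the intervention ends (7.2).

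It is also fair to say that stopping at IUC replacement cannot undo a capsule taken an hour earlier. Section 2.0 puts steady state at the fifth day of dosing, so an active-arm subject on schedule already has drug on board. That limits the benefit of the change and is why an interval is needed as well as a stop.

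**Conclusion.** The point holds as a cheap improvement. The plan permits a capsule after the catheter has been replaced and does not require study drug to stop before a clinical alpha-blocker is started. A blinded team following the text could therefore give a combination that section 9.1.8.1 says to avoid.

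The size is small: normally one capsule per subject, two in an edge case, with pharmacological exposure only in the tamsulosin arm. Frequency cannot be estimated, because the documents give no rate of IUC replacement or of rescue alpha-blocker use. The sample size is unaffected.

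This rests on two assumptions. The range of evening dosing hours is assumed, as marked above. The appended bladder management protocol, of which only the starting conditions could be read, is assumed not to govern study-drug dosing; it is described as institutional standard of care.

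**What to change.** 1. In 7.1.1, 5.6.3 and 7.5, state that no study capsule is given once an IUC has been replaced for retention.
2. In 7.5, cross-reference 4.2.2.4.1 and require that study drug is stopped before any clinical alpha-blocker is started; that the first dose of that drug is given no earlier than the next scheduled evening dose time, about 24 hours after the last capsule; and that every subject is treated as possibly on tamsulosin.
3. State that stopping study drug in this way neither ends follow-up nor removes the subject from the intent-to-treat analysis. UTI to 30 days, length of stay and discharge with an IUC may still be pending, and the withdrawal wording of 4.2.2.4.1 could be taken to end their collection.

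The choice of rescue drug should stay with the treating team.

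The cost is a few sentences and normally one capsule per affected subject. No unblinding is needed. The downside is a possible wait for rescue, less than a day at a fixed dosing hour, with the catheter in place. Residual drug from a capsule taken before the catheter was replaced is reduced but not eliminated.

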7.2 Adverse Event Reporting Requirements

An adverse event log will be maintained for each enrolled subject. Adverse event screening will occur at three time points: 1) on the day of surgery either pre- or post- operatively (in person, in the hospital, via interview of the subject by a study team member), 2) during the postoperative period for the period from surgery until 48 hours after completion of the intervention (via abstraction of AEs from the subject's EMR), and 3) 30-40 days after surgery (via telephone interview of the subject by a study team member). Safety data will be monitored and analyzed by an external Data Monitoring Committee (through ICTR), and unanticipated problems or complications will be reported to the IRB per its reporting guidelines. Unexpected or severe adverse events will also be reported to the PI within 72 hours of identification.

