5.3 Data collection

At the time of the pre-operative visit, following enrollment in the study, subjects will fill out the International Prostate Symptom Score (IPSS) Survey. This survey is a validated, selfadministered 7-item questionnaire that assesses obstructive lower urinary tract symptoms. Additionally, subjects will be administered a questionnaire that asks about history of prior problems with urinary retention and prior urinary tract surgeries or procedures, consisting of a total of 3 questions. Subjects may decline to answer the survey questions on the IPSS survey, but this will result in ineligibility for the trial, as IPSS score is a stratification variable for randomization. Subjects may skip the urinary tract surgery/history questions if they feel uncomfortable or embarrassed, and this will not result in exclusion from the study. Case report forms (CRFs) will be utilized to collect data prospectively during the subject's postoperative course while inpatient. This data will be collected by a study team member, and will include time of arrival and departure from the operating room, time of first void, date/time of IUC removal, date/time of first void after catheter removal, first post-void residual volume, date/time of first straight catheterization (if applicable), date/time of all subsequent straight catheterizations (if applicable), date/time of IUC replacement (if applicable), and date/time of the first two adequate voids (if applicable). Finally, subjects will be contacted by telephone 30-

40 days after the date of surgery to ask if they have been treated for a urinary tract infection since discharge from the hospital (in order to capture UTIs that are diagnosed outside of our hospital system). Additionally, data regarding adverse events will be collected using an Adverse Event Log. A study team member will make contact with the subject at two separate time points to inquire about adverse events: 1) on the day of surgery (in person, in the hospital), and 2) postoperatively via telephone call 30-40 days after surgery. Additionally, adverse events will be abstracted from the electronic medical record during the immediate postoperative period. AEs occurring following surgery up until 48 hours after discontinuing study drug will be abstracted from the subject's EMR.

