7.3 Dose Modifications

Dose modifications will not be made in this study. If a subject has an intolerable adverse event or side effects related to the study treatment, the drug will be discontinued and the subject will be removed from the protocol. Follow up outcome data will still be collected to allow for intent-to-treat analysis.

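### Chart review for adverse events covers an outcome-dependent period of about 2 to 8 days after surgery, so ascertainment probably differs between the arms

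*Combined protocol and SAP*

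**What the plan says.** Section 7.2 screens for adverse events three times: an interview on the day of surgery, abstraction from the electronic medical record (EMR), and a telephone interview 30-40 days after surgery. Only the EMR abstraction has a variable end. Section 7.2 places it "during the postoperative period for the period from surgery until 48 hours after completion of the intervention". Section 5.3 words the end by study drug: "AEs occurring following surgery up until 48 hours after discontinuing study drug will be abstracted from the subject's EMR". Sections 8.0 and 13.0 repeat the 48-hour rule.

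What ends the intervention is set out elsewhere:

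- Recovery (section 7.5): "Treatment will be discontinued within 24 hours of the subject's completion of the bladder management protocol with return of normal bladder function", meaning two successive voids each leaving a residual under 200 mL.
- Catheter replacement (section 5.6.3), for a subject who "OR requires replacement of an IUC, the treatment will be discontinued within 24 hours, and the protocol is complete".
- Discharge (section 7.1): "No subjects will be discharged from the hospital on study medication".
- An intolerable adverse event (section 7.3): "the drug will be discontinued and the subject will be removed from the protocol".
- Otherwise the 14th dose, on the evening of postoperative day (POD) 6.

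Section 5.6.3 allows completion as early as POD0.

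The scope of the telephone call is described in two ways. Section 5.6.5 says it is "to inquire about adverse events since discharge from the hospital". The table in section 8.0 gives it the whole post-intervention phase, up to 30 days after surgery. Sections 5.3, 5.6.4 and 7.2 do not limit the call to events after discharge.

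Section 3.4.2.2 makes adverse events a secondary endpoint. Section 10.10 assigns binary secondary outcomes to chi-squared or Fisher's exact tests and describes no adjustment for length of observation.

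**The concern.** The length of chart review is a consequence of treatment response. A subject who recovers on POD0 has about 2 days of abstraction, and one who is still retaining at the last dose has about 8. The deciding events, recovery of voiding and catheter replacement, lie close to the primary endpoint, and section 10.8 hypothesizes that tamsulosin changes both. A crude comparison of adverse event proportions would then mix a drug effect on adverse events with a drug effect on how long the chart is read.

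Section 10.8.2.2 expects more dizziness and orthostasis on tamsulosin. A shorter reading period in that arm would work against finding them.

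The telephone call adds a second weakness. If it covers only events since discharge, inpatient days after the 48-hour limit belong to no screening. If it covers the whole post-intervention phase, those days rest on recall weeks later and not on the chart.

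**Working it through.** **The plan's own figure.** The documents give no time-to-completion data and no expected window length by arm. The one stated figure that uses the relevant rates is the sample size in section 10.2: 30% versus 15%, two-sided alpha 0.05, 80% power, 134 per arm. The usual two-proportion formula gives 121 per arm without continuity correction and 134 with it. The figure reproduces, so 30% and 15% are used below.

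**Range of the window.** Completion on POD0 plus 48 hours gives about 2 days. The last dose on POD6 plus 48 hours gives about 8 days.

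**Difference between arms.** Let *b* be the mean window in days of a subject without retention, *x* the mean extra days for a retained subject, and *p* the retention rate. Both *b* and *x* are assumptions.

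- Mean window in an arm = *b* + *p·x*
- Placebo minus tamsulosin = (0.30 − 0.15)·*x* = 0.15·*x*

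For the effect on recorded events, assume the same true hazard *h* in both arms, 2% to 5% per day (not from the documents), and count chart-window events only:

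- Difference in recorded proportion = 0.15·(e^(−hb) − e^(−h(b+x)))
- Example with *b* = 2, *x* = 6, *h* = 0.05: 0.15 × (0.905 − 0.670) = 0.035, or 3.5 points

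| b | x | Placebo, days | Tamsulosin, days | Gap, days | Spurious difference, points (h = 2% to 5%) |
|---|---|---|---|---|---|
| 2 | 1 | 2.30 | 2.15 | 0.15 | 0.3 to 0.7 |
| 2 | 2 | 2.60 | 2.30 | 0.30 | 0.6 to 1.3 |
| 3 | 3 | 3.90 | 3.45 | 0.45 | 0.8 to 1.8 |
| 2 | 4 | 3.20 | 2.60 | 0.60 | 1.1 to 2.5 |
| 2 | 6 | 3.80 | 2.90 | 0.90 | 1.6 to 3.5 |
| 3 | −1 | 2.70 | 2.85 | −0.15 | −0.3 to −0.7 |

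The row with *x* = 6 is the extreme, in which every retained subject reaches the 14th dose. There the tamsulosin window is 0.9/3.8 = 24% shorter. In the last row retained subjects leave early through catheter replacement, and the sign reverses. The model holds *b* equal in both arms, so faster recovery among tamsulosin subjects without retention would add to the gap.

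**Stopping boundary.** Section 9.1.10 reports syncope of 0.2% on tamsulosin and 0.6% on placebo, and puts priapism at probably under 1 in 50,000. Even if all 0.6% fell inside the chart window, the extreme 24% shortening moves it by 0.6 × 0.24 = 0.14 points. The boundary is an excess of 5 points in section 13.1 and 10 points in section 10.6. Those two sections must be reconciled, but that is a separate matter.

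**The case against.** Three stronger readings are tempting, and the documents support none of them.

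*Tamsulosin will look safer by construction.* Catheter replacement also closes the window, and section 10.8.2.1 expects it more often on placebo. The direction is probable but not built in. Reversal, however, needs retained subjects to finish earlier on average than those without retention. That the window depends on outcome is certain either way.

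*Adverse events are lost.* This follows only from the wording of section 5.6.5. The table in section 8.0 covers the same days through the call. What stands is an inconsistency between the two, and telephone recall in place of chart review for some inpatient days.

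*The safety boundary is compromised.* At the quoted syncope rates the shift is negligible. Section 13.1 also sends all serious adverse events to the monitoring committee with no 48-hour limit.

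It can fairly be added that two of the three screenings have the same timing in both arms, that at least 7 of the 7 to 14 doses are taken before surgery, and that last dose plus 48 hours is a reasonable treatment-emergent rule in which shorter observation goes with shorter exposure. All of this stands and limits the size of the problem. It does not justify comparing crude proportions over windows of unequal length.

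**Conclusion.** The point holds as a minor, inexpensive improvement. The chart-review window varies from about 2 to 8 days with a post-randomization outcome close to the primary endpoint, and the plan makes no allowance for this. On the trial's own hypotheses the window is probably shorter on tamsulosin.

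The size cannot be derived from the documents. It is 0.15·*x* days, at most 0.9 day in the range examined. Under the assumed equal hazards the spurious advantage to tamsulosin runs from 0.3 points (*x* = 1) to 3.5 points (*x* = 6), with a small reversal possible. These are upper figures for each scenario, because they give the other two screenings no credit for events outside the chart window. They concern adverse events as a whole and should not be carried over to syncope or priapism.

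**What to change.** 1. Abstract adverse events from the EMR for every subject over one fixed period from surgery, for example through POD8 (48 hours after the last possible dose), whenever drug stops. Do not truncate at discharge: section 10.8.2.8 hypothesizes a shorter stay on tamsulosin, so a discharge limit would bring back an arm-dependent window.
2. Have the telephone call cover all days after discharge, since the hospital record alone may miss events at home or elsewhere.
3. Reconcile section 5.6.5 with section 8.0 so that no inpatient day falls outside both screenings, and use one description of the abstraction window in sections 5.3, 7.2, 8.0 and 13.0.
4. If wanted, keep the events up to 48 hours after the last dose as a supplementary treatment-emergent analysis.

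The cost is protocol wording and a few extra days of chart abstraction per subject by the same staff. No dose or clinical rule changes.
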